**12.2.2 Cutaneous T-cell Lymphoma (CTCL) Response Criteria**

Dermatologic responses will be determined by the modified Severity-Weighted Assessment Tool (mSWAT), a standardized approach to measuring the extent and severity of overall skin disease in patients with CTCL. It will be briefly described and full details are provided in Appendix I. The purpose of this description is to optimize intra-observer objectivity and to minimize the potential for intra-observer and inter-observer variability in the measurement of overall skin disease. Only physicians who received training will be permitted to conduct mSWAT assessments during the clinical study. It is essential that physicians adhere as closely as possible to the prescribed procedures so as to reduce measurement error and variability. All efficacy assessments should be performed by the same physician for each patient whenever possible. Physicians will be instructed not to examine previous mSWAT assessments and full body photographs prior to conducting the current mSWAT assessment.

**1. Total Body Surface Area (TBSA) Involvement by Skin Disease**

The body is divided into 12 regions with pre-assigned %TBSA based on the burn literature. The extent of skin disease in each region is quantified by using the patient's palm to measure the %TBSA involvement within region: patient's palm with 4 fingers (excluding the thumb) is 1% of TBSA. Patient's palm without fingers is 0.5% of TBSA. The patient's palm with 4 fingers is traced on a transparency sheet at the baseline visit, using a permanent marker that will not rub off or smear. The transparency of the patient's palm should be used in all mSWAT assessments during the course of the clinical study. The transparency will be labeled with the patient's study ID number kept in the patient's study file on site. Using the baseline visit transparency of the patient's palm, the investigator will measure and record on

the case report form (Example of table from CRF is given below) the %TBSA for each lesion type within each of the 12 regions.

## 2. Severity Weighting Factor

The severity weighting factors will be the following:

- 1= patch (flat erythema or erythema with mild infiltration)
- 2=plaque (elevated erythema or erythema with moderate infiltration)
- 4=tumor or ulceration (erythema with fissuring, ulceration or tumor)

Patch is defined as abnormal skin not elevated from normal skin. A plaque is defined as abnormal skin elevated from normal skin by < 5 mm. A plaque elevated  $\geq$ 5 mm is a tumor.

## 3. Calculating Skin Scores

The sum of %TBSA by lesion is derived by summing the %TBSA from all regions affected by the lesion. The sum of %TBSA across lesion types (patches, plaques and tumors) within each region cannot exceed the %TBSA for the region. For example, the %TBSA for the head region is 7%. The sum of %TBSA across lesion types from head can only range from 0-7%. The skin score subtotal by lesion type are derived by multiplying the sum of %TBSA for patches from all regions by 1, sum of %TBSA of plaques from all regions by 2, and the sum of %TBSA of tumors or ulcers from all regions by 4. The skin score total is derived from summing the skin score subtotals for patches, plaques and tumors or ulcers. The skin score total is dimensionless with a scale of 0 to 400.

Region	% TBSA for the region	% TBSA Patch (or flat erythema)	% TBSA Plaque (or elevated/indurated erythema)	% TBSA Tumor/ Ulceration (or erythema w/fissuring, ulceration)
Head	7			
Neck	2			
Anterior Trunk	13			
Posterior Trunk	13			
Buttocks	5			
Genitalia	1			
Upper Arms	8			
Forearms	6			
Hands	5			
Thighs	19			
Lower Leg	14			
Feet	7			
% BSA by category	100			
Severity Weighting Factor		X 1	X 2	X 4
Skin Score Subtotal				

Responses will be determined by the criteria described in the table below. Progression of disease while on treatment should be confirmed by a second

assessment 1-4 weeks later so that patients who experience a temporary flare of disease due to skin infection or other intercurrent illnesses are not removed from the study prematurely.

Assessment	Description	Status
Completely clear	No evidence of disease; 100% improvement	CR
Marked Improvement	Greater than or equal to 50% decrease in skin scores compared	PR
Slight Improvement	Less than 50% decrease in skin scores compared to baseline	SD
Worse	
≥25% increase in skin scores compared to baseline while the patient is actively taking the study drug or ≥50% increase in the sum of the products of the greatest diameters of pathologically positive lymph nodes (should be documented by biopsy) compared to baseline while the patient is actively taking the study drug.
	PD

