## **6.0 CRITERIA FOR SUBJECT ELIGIBILITY.**

### **6.1 Subject Inclusion Criteria**

1. Pathology confirmed lymphoma or multiple myeloma.
  - Hodgkin lymphoma is eligible for either phase and will be considered a B-cell lymphoma in the phase IIa study.
  - Phase IIa portion, subjects must have B-cell lymphoma, T-cell lymphoma, or multiple myeloma.
2. Relapse or progression after at least 1 systemic therapy.
3. Measurable disease for phase IIa portion only.

- Lymphoma (includes CTCL patients who are NED in skin): CT or PET/CT by modified Cheson criteria with incorporation of PET.
  - Multiple myeloma: Patient must have measurable disease and therefore must have at least one of the following:
    - i. Serum M-protein  $\geq 0.5\text{gm/dL}$  ( $\geq 5\text{gm/L}$ )
    - ii. Urine M-protein  $\geq 200\text{mg/24hr}$
    - iii. Serum FLC assay: involved FLC  $\geq 10\text{mg/dL}$  ( $\geq 100\text{mg/L}$ ) provided serum FLC ratio is abnormal.
  - CTCL: mSWAT  $>0$ , or absolute Sezary count  $\geq 1000\text{ cells}/\mu\text{L}$ .
4. Age  $\geq 18$  years at the time of signing the informed consent form.
  5. Able to adhere to the study visit schedule and other protocol requirements.
  6. Previous systemic anti-cancer therapy must have been discontinued at least 3 weeks prior to treatment in this study. If there is progression of disease on that therapy and all adverse effects have resolved to Grade 1 or baseline, in which case 2 weeks is acceptable.
  7. Previous radiation, hormonal therapy, and surgery must have been discontinued or completed at least 2 weeks prior to treatment in this study and adverse effects must have resolved. Lymph node or other diagnostic biopsy within 2 weeks is not considered exclusionary.
  8. Short course systemic corticosteroids for disease control, improvement of performance status or non-cancer indication (< 7 days) must have been discontinued at least 7 days prior to study treatment. Stable ongoing corticosteroid use ( $\geq 30$  days) up to an equivalent dose of 15 mg of prednisone is permissible.
  9. ECOG performance status of  $\leq 2$  at study entry (see Appendix A).
10. Laboratory test results within these ranges:
- Absolute neutrophil count  $\geq 1.0/\text{mm}^3$ .
  - Platelet count  $\geq 70\text{ K}/\mu\text{L}$ , if thrombocytopenia is due to bone marrow involvement platelet count must be  $\geq 50\text{ K}/\mu\text{L}$ .

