 Lymphoma: CT including at least the chest, abdomen and pelvis or PET/CT is required for response (systemic B and T-cell lymphoma patients only) assessment. A bone marrow will only be repeated to confirm a complete response if previously known to be involved. Cutaneous T-cell lymphoma patients will have imaging at baseline and (CTCL) will have an mSWAT (Appendix I) performed monthly for the first three cycles and then at each response assessment timepoints (end of cycle 4, 6 and thereafter at the end of every third cycle). In CTCL patients, imaging will be repeated if appropriate (patients with known nodal or visceral disease) every other cycle. Sezary panel in patients with Sezary syndrome. Cutaneous lymphoma patients without nodal or visceral disease will have imaging repeated only to confirm a complete response. After cycle 12, patients on continuous therapy may be imaged as clinically indicated, at the discretion of the treating physician. At discontinuation of therapy, end of study response assessments – including imaging – should be performed.

Serum/urine protein electrophoresis, serum/urine immunofixation, quantitative immunoglobulins, and serum free light chains are required if appropriate for (multiple myeloma patients only) response assessment. A bone marrow will only be repeated if to confirm a complete response. Patients with non-secretory myeloma will have the bone marrow assessment repeated if they have been otherwise clinically stable (i.e. without new lytic lesions, soft-tissue plasmacytomas or hypercalcemia). A skeletal survey is allowed to rule out bone lesions for evaluation of disease progression and to confirm a complete response in nonsecretory multiple myeloma. PET/CT should be performed at screening and to confirm responses in patients with soft tissue plasmacytomas.

 An additional safety assessment will be done 28 days (+/- 2 days) following the last dose of protocol therapy.

 If romidepsin is omitted on day 8 per dose reduction algorithm (Table 4) then hematologic and electrolyte assessments are not required.

Response assessment will be performed at the end of cycles 2, 4, and 6. Thereafter, response assessment will occur at the end of every third cycle (9,12,15, etc.) until disease progression or removal from study. Myeloma patients will have their disease assessed after each cycle.

 +/- 3 days

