#### **Partial Remission (PR):**

- Greater than or equal to 50% decrease in SPD of the six largest dominant nodes/nodal masses.

- No increase in size of other nodes, liver or spleen.
- Splenic and hepatic nodes regressed at least 50% in SPD.
- No new sites of disease.
- Bone marrow and organs other than the spleen and liver cannot be considered for evaluation for PR because involvement at these sites is considered evaluable but not measurable.

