True toxicity rate	5%	10%	15%	20%	25%	30%	35%	40%	50%
Dose reduction prob.	0.000	0.000	0.001	0.004	0.016	0.056	0.118	0.243	0.632

18 months after the final patient is enrolled and after 80% of patients, MSKCC will analyze disease status, serious adverse events and survival for all patients.

Secondary objectives of this study aim at examining many clinical endpoints (see Sections 4 and 12 for detailed definitions). Overall response rate (ORR) and clinical benefit rate (CBr) for MM patients, complete response rate, very good partial response/partial response rate will be summarized using proportions and confidence intervals will be provided. Time to response, duration of response and event free survival will be analyzed by routine survival analysis tools such as Kaplan-Meier estimation or competing risks method. In this portion of the study, all three disease subtypes (B-cell lymphoma, multiple myeloma, PTCL) will be grouped together including those from the phase Ib that were treated at MTD. Note that the response criteria are different among the disease subtypes (see Section 12.0). To preliminarily collect the data, subset analyses will also be conducted to evaluate the ORR, TTR, DOR, and EFS for each disease subtype.

To further investigate activity of this regimen in patients with acute T-cell leukemia/lymphoma, an additional cohort of 6 patients will be added to the phase IIa portion of the study. When the true response rate is 30% or above, the probability that none of the 6 patients will respond is less than 0.12. Subset analyses will be conducted to evaluate the ORR, TRR, DOR, and EFS for each disease subtype.

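### Blood disease can qualify a CTCL patient for phase IIa, but no PR, SD or PD rule for CTCL or ATLL scores it, and a patient entered on Sezary count alone cannot be scored for them

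*Combined protocol and SAP*

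**What the plan says.** **Entry.** Section 6.1 sets the requirement "Measurable disease for phase IIa portion only". For CTCL it is met by an mSWAT above 0 "or absolute Sezary count" of at least 1000 cells/µL, so blood disease alone is enough. For other lymphoma, and for CTCL with no disease in the skin, measurability is by CT or PET/CT.

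**Assessment.** Section 8.1 requires a baseline Sezary panel in Sezary syndrome. Footnote 7 of the Table 7 legend, on response assessment, lists "Sezary panel in patients with Sezary syndrome" alongside mSWAT and imaging. Table 7 schedules hematology throughout treatment.

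**CTCL response (Section 12.2.2).** Responses are to be determined by the table that closes the section:
- CR: completely clear, described as "No evidence of disease; 100% improvement".
- PR: a fall of at least 50% in skin score.
- SD: a fall of less than 50% in skin score.
- PD: a rise of at least 25% in skin score, or of at least 50% in the summed products of diameters (SPD) of positive nodes.

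**ATLL.** Section 14.0 says that "an additional cohort of 6 patients will be added to the phase IIa portion of the study", to investigate activity further. There are no ATLL-specific response criteria, so Section 12.2.1 applies. Its CR requires absence of clinical, radiographic and diagnostic evidence of disease, with conditions on nodes, spleen, marrow, PET and biochemistry. Its PR rests on nodes, liver, spleen and absence of new sites, and "Bone marrow and organs other than the spleen and liver cannot be considered for evaluation for PR". Its PD is nodal SPD growth or a new lesion.

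**Endpoints (Section 4.1).** ORR counts best response at any assessment. DOR and EFS end at progression, change of therapy or death. Section 14.0 plans ORR, DOR and EFS by disease subtype.

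**The concern.** The plan treats blood as a disease site when it admits a CTCL patient and when it lists tests, but not when it assigns PR, SD or PD. This goes beyond missing detail: the Section 12.2.2 table is stated as the rule, and following it gives the wrong category for patients whom the plan admits. By contrast, the myeloma PD definition in Section 12.1.1 covers serum, urine, light chains, calcium, bone and plasmacytomas.

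At stake are the T-cell and ATLL estimates of ORR, DOR and EFS, and the CR rate if the CR wording is read loosely. Section 4.1 says phase IIa is meant to give background for a possible subtype-specific phase II study, and these are the figures that study would use.

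**Working it through.** **1. Apply the rules to the patients who can enter.**

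| Patient | Rule as written | Result |
|---|---|---|
| CTCL, skin and blood; skin score down 50%, Sezary count rising | PR on skin score only | PR, counted in ORR |
| CTCL, skin and blood; skin and nodes stable, Sezary count rising | PD on skin score or nodal SPD | Not PD; no progression event for DOR or EFS |
| CTCL entered on Sezary count, mSWAT 0, no involved nodes | Percent change from a zero baseline | PR, SD and PD cannot be scored |
| CTCL, skin cleared, Sezary count still high | Completely clear and no evidence of disease | Ambiguous |
| ATLL, nodes and blood; nodal SPD down 50%, circulating disease rising | PR on nodes, liver, spleen, no new sites | PR, counted in ORR |
| ATLL, circulating disease rising, nodes stable, no new lesion | PD on nodal SPD or new lesion | Not PD |

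For the third row, percent change is (current − baseline)/baseline. With baseline 0 the denominator is 0, so neither the 50% fall nor the 25% rise is defined. The nodal limb of PD helps only where nodes are involved.

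**2. Reproduce the plan's own figure.** Section 14.0 says that, at a true response rate of 30% or above, "the probability that none of the 6 patients will respond is less than 0.12". At 30%, 0.7^6 = 0.1176. The figure is correct.

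**3. Effect of one misclassified response.**
- T-cell cohort of 15: 1/15 = 6.7 points.
- ATLL cohort of 6: 1/6 = 16.7 points. The exact 95% interval moves from 0–45.9% (0/6) to 0.4–64.1% (1/6).
- Pool of about 44: 1/44 = 2.3 points.

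**4. How many patients could be affected.** T-cell plus ATLL patients are 15 + 6 = 21 of about 44 (Section 14.0). The documents do not say how many will have CTCL, Sezary syndrome or circulating ATLL, so 21/44 is a ceiling.

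**5. Illustration on assumed rates.** The documents give no false-response rate. Let f be the assumed chance that an ATLL patient is called a responder although an all-compartment definition would not agree, and suppose that no patient truly responds by that definition. Then P(at least 1 of 6) = 1 − (1 − f)^6:
- f = 5%: 1 − 0.95^6 = 26%
- f = 10%: 1 − 0.90^6 = 47%
- f = 20%: 1 − 0.80^6 = 74%

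These show sensitivity only. They do not estimate the error rate in this trial.

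**The case against.** The other side has good points, and several limit the claim.

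- **CR.** A reader might infer that a patient with clear skin and a high Sezary count is a CR. The documents do not support this. The CR row asks for no evidence of disease, Section 12.2.1 asks for none on clinical, radiographic or diagnostic grounds, and a Sezary panel is listed for response. The wording is ambiguous, since no blood threshold is given, but it does not grant CR.
- **Baseline mSWAT 0.** A reader might infer that this patient counts as completely clear from the start. A zero baseline cannot show 100% improvement, and a qualifying Sezary count is itself evidence of disease. The patient is unscorable, not an automatic CR.
- **ATLL.** It would be too strong to say that ATLL is scored only on skin or nodes. Section 12.2.1 also uses liver, spleen, marrow, PET and biochemistry. None of its PR or PD criteria is a circulating-disease criterion. Purely leukemic ATLL may not meet CT or PET/CT measurability, so the exposure is mainly mixed nodal and blood disease.
- **DOR and EFS.** Blood progression that leads to a change of therapy or death does end both. What remains is delay, or a missed event where neither follows.
- **Central review.** Section 16.1.2 makes responses subject to committee review with additional laboratory reports. This helps, but the committee has no written blood criterion to apply.
- **The six-patient cohort.** Section 14.0 states one probability and then descriptive subset analyses. It sets no decision rule of zero versus at least one response. A nodal response that ignores blood still needs a 50% reduction, so the illustration does not describe a wholly inactive regimen.

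The gap for PR, SD and PD stands after all of these.

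**Conclusion.** The point holds for PR, SD and PD in CTCL with blood involvement, and for PR and PD in ATLL with circulating disease. For CR the text is ambiguous. In mixed disease the bias in ORR, DOR and EFS is upward. In blood-only patients its direction is unclear, because a true blood response is as unscorable as a blood progression.

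Each misclassified response is worth 6.7 points in a 15-patient cohort and 16.7 points in the ATLL cohort. The total effect cannot be computed, because the number of patients with blood involvement is not given. A reader might take 21/44 as the affected share, or 47% as the chance of a false ATLL signal. The first is only a ceiling, and the second is one value in an assumed range of 26% to 74%.

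Response is a secondary objective and the subtype analyses are exploratory. The MTD and safety conclusions are unaffected. The plan should still be changed before responses are analyzed.

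**What to change.** For the analysis of ORR, CR rate, DOR and EFS, reconcile the entry rule in Section 6.1 and the panel in Table 7 footnote 7 with the response definitions in Sections 12.2.1 and 12.2.2:

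1. Add a blood-compartment response category for Sezary syndrome and ATLL, with thresholds chosen by the sponsor.
2. Add a global-response derivation across the compartments involved at baseline. CR requires clearance of every involved compartment, including blood. A skin or nodal PR does not count as a response if blood disease has progressed. Blood progression counts as a progression event in the endpoint derivation.
3. Score patients with baseline mSWAT 0 on the Sezary count.
4. Use the Sezary panel, CBC, mSWAT and imaging already collected. For ATLL, where no Sezary panel is specified, use the scheduled CBC.

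This concerns endpoint derivation only. Section 13.1 ends treatment at disease progression, so the sponsor must reconcile any effect on when treatment stops; none is prescribed here.

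The cost is a paragraph in Section 12 and a CRF derivation. Reported response rates may be lower. Under step 2, a nodal or skin PR with unchanged blood disease would still count as a response, so the sponsor should state that openly.

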## 13.0 CRITERIA FOR REMOVAL FROM STUDY

### 13.1 Discontinuation of Study Treatment

Treatment will continue until the occurrence of any of the following events.

- Disease progression
- Adverse event(s) that, in the judgment of the Investigator, may cause severe or permanent harm or which rule out continuation of the treatment regimen.
- Discontinuation of lenalidomide or romidepsin for any reason.
- Major violation of the study protocol.
- Withdrawal of consent
- Lost to follow up
- Death
- Pregnancy or a positive pregnancy test

## 14.0 BIOSTATISTICS

The standard dose-escalation scheme for this study is as follows. Patients will be accrued to the study in cohorts of 3. For any given dose an initial cohort of 3 patients will be treated at that dose. The dose level will be escalated if none of the 3 patients exhibits any DLT in the first cycle as defined in section 4.1. If a DLT is observed in one patient, an additional cohort of 3 patients will be treated at that dose. The dose will be escalated if none of the additional 3 patients exhibits any DLT. Dose-escalation stops and the previous dose will be considered the MTD if 2 or more patients have a DLT. If the previous dose level has been administered to only 3 patients, an additional 3 patients will be enrolled to confirm the result. For this design the probability of escalation is as follows:

True toxicity rate	5%	10%	15%	20%	25%	30%	40%	50%
Probability of escalation	0.97	0.91	0.81	0.71	0.60	0.49	0.31	0.17

Dose escalation will start with dose level 1. A dose level -1 is also added to the design to ensure a minimum level of toxicity (we expect this dose level will be quite tolerable for patients). The maximum number of patients needed for this dose escalation design is 30. Patients with measurable disease treated at MTD in the phase Ib will be analyzed in phase Ila to further characterize the toxicity of romidepsin and lenalidomide in combination at the MTD determined by phase Ib. In phase Ila, we plan to enroll about 39 patients so that the total number of patients to be treated at MTD will be approximately 44 (we plan to enroll 15 patients with B-cell lymphomas, 8 patients with multiple myeloma, 15 patients with T-cell lymphomas and additional 6 patients with acute T-cell leukemia/lymphoma). To subsequently monitor the safety primary endpoint in the phase Ila portion, we will employ a dose-reduction plan for the predefined DLT in the phase Ib portion during cycles 1-4. This dose-reduction plan specifies that the dose will be reduced from the phase Ib MTD to the MTD-1 (10mg/m^2 romidepsin; 25mg lenalidomide) if DLT occur in cycle 1-4 in: ≥8/first 15; ≥16/first 30; or if more than 24 patients when the last (45th) evaluable patient has completed the trial have any DLT. If at MTD-1 a DLT occurs in ≥8/first 15; ≥16/first 30, then MTD-2 (8mg/m^2 romidepsin; 25mg lenalidomide) will be employed for the remainder of phase Ila. The probability of dose-reducing from the MTD is the following:

True toxicity rate	5%	10%	15%	20%	25%	30%	35%	40%	50%
Dose reduction prob.	0.000	0.000	0.001	0.004	0.016	0.056	0.118	0.243	0.632

18 months after the final patient is enrolled and after 80% of patients, MSKCC will analyze disease status, serious adverse events and survival for all patients.

Secondary objectives of this study aim at examining many clinical endpoints (see Sections 4 and 12 for detailed definitions). Overall response rate (ORR) and clinical benefit rate (CBr) for MM patients, complete response rate, very good partial response/partial response rate will be summarized using proportions and confidence intervals will be provided. Time to response, duration of response and event free survival will be analyzed by routine survival analysis tools such as Kaplan-Meier estimation or competing risks method. In this portion of the study, all three disease subtypes (B-cell lymphoma, multiple myeloma, PTCL) will be grouped together including those from the phase Ib that were treated at MTD. Note that the response criteria are different among the disease subtypes (see Section 12.0). To preliminarily collect the data, subset analyses will also be conducted to evaluate the ORR, TTR, DOR, and EFS for each disease subtype.

To further investigate activity of this regimen in patients with acute T-cell leukemia/lymphoma, an additional cohort of 6 patients will be added to the phase IIa portion of the study. When the true response rate is 30% or above, the probability that none of the 6 patients will respond is less than 0.12. Subset analyses will be conducted to evaluate the ORR, TRR, DOR, and EFS for each disease subtype.

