**\*1 cycle equals 28 days**

### **9.3 Treatment Plan romidepsin/lenalidomide Phase IIa**

The entire accrual is planned to have up to 51 patients in the phase IIa portion; each disease cohort will have 15 patients (B-cell lymphoma, multiple myeloma or PTCL). There will be an expansion of the T-cell cohort to include an additional 6 patients with acute T-cell leukemia/lymphoma. After a sufficient number of patients have been enrolled for determination of the primary and secondary objectives, cohorts may be closed to accrual by the MSK principal investigator. The MTD for lymphoma has been determined to be 14mg/m^2 romidepsin on Days 1, 8, 15 and 25mg lenalidomide from Days 1-21. The patients treated at MTD in the phase Ib cohort (if measurable disease at enrollment) and phase IIa cohort will be evaluated both collectively and by disease subtype. Patients with more than one histology are eligible and will be assigned by the principal investigator to a specific disease subtype.

- In patients with MM, due to the presence of toxicities, patients will be dosed at romidepsin 10mg/m^2 and lenalidomide 25mg (see table 2a). If two of six (or fewer) patients treated at this dose level develop dose-limiting toxicities, the initial dosing for subsequent patients will be decreased to romidepsin

10mg/m^2 and lenalidomide 15mg. For example, if two of four patients treated at this initial dose develop dose-limiting toxicities, the starting dose for subsequent patients will be reduced as above.

- At a starting dose of romidepsin 10mg/m^2 and lenalidomide 15mg, should 2 of 6 (or less) patient will be reduced to romidepsin 8mg/m^2 and lenalidomide 15mg.
- At a starting dose of romidepsin 8mg/m^2 and lenalidomide 15mg, should 2 of 6 (or less) patients have dose-limiting toxicities, the initial dose for subsequent patients will be reduced to romidepsin 8mg/m^2 and lenalidomide 10mg.

Table 2a: Multiple Myeloma Dosing for Phase IIa Portion

Dose level	Romidepsin	Lenalidomide
1	10	25
-1	10	15
-2	8	15
-3	8	10

The treatment plan for the phase IIa portion is described below:

Romidepsin/Lenalidomide Cycle 1 Day 1 + subsequent Cycle X

Romidepsin MTD IVPB over 4 hours

Lenalidomide MTD PO q days 1-21

Romidepsin/Lenalidomide Cycle 1 Day 8

Romidepsin MTD IVPB over 4 hours

Romidepsin/Lenalidomide Cycle 1 Day 15

Romidepsin MTD IVPB over 4 hours

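### Section 14 counts myeloma patients as treated at the MTD although section 9.3 starts them one level lower; about 36 are planned at 14/25, the 45-patient look cannot trigger for them, and the stated 0.632 is not achieved

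*Combined protocol and SAP*

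**What the plan says.** Section 14.0 states "In phase Ila, we plan to enroll about 39 patients" and that "the total number of patients to be treated at MTD will be approximately 44". It breaks the 44 down as 15 B-cell lymphoma, 8 myeloma, 15 T-cell lymphoma and 6 acute T-cell leukemia/lymphoma. To monitor the primary safety endpoint it sets one rule on DLTs in cycles 1 to 4. The dose drops from the phase Ib MTD to MTD-1 (10 mg/m² plus 25 mg) at 8 or more DLTs in 15 patients, at 16 or more in 30, or at over 24 once the last, 45th, "evaluable patient has completed the trial have any DLT". One row of reduction probabilities follows, under a single DLT rate and ending at 0.632 for a 50% rate.

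Section 9.3 differs. "The MTD for lymphoma has been determined to be" 14 mg/m² plus 25 mg. "In patients with MM, due to the presence of toxicities, patients will be dosed at romidepsin" 10 mg/m² with lenalidomide 25 mg. Myeloma has its own dose ladder (Table 2a, "Multiple Myeloma Dosing for Phase IIa Portion") and steps down when 2 of up to 6 patients have a DLT. The section's totals also differ from section 14.0: "The entire accrual is planned to have up to 51 patients in the phase IIa portion", and "each disease cohort will have 15 patients (B-cell lymphoma, multiple myeloma or PTCL", plus the 6 additional patients.

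**The concern.** Phase IIa myeloma patients start at the dose that the section 14.0 rule would reduce to. They cannot be counted as treated at the MTD, nor can they be reduced from it. Two things follow. First, fewer patients are planned at 14/25 than the 45 on which the rule and its probability row rest. Second, nothing states whether a myeloma DLT at 10/25 counts towards the looks at 15 and 30. Section 9.7 refers the whole phase IIa portion to section 14.0 for its toxicity rule, while section 9.3 gives myeloma a separate one. Even the next step down from 10/25 differs: section 14.0 goes to 8/25, Table 2a to 10/15.

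At stake is the stated safety rule for the lymphoma MTD. Two teams could count different patients at the same look and reach different dose decisions, and the plan states more protection at a 50% DLT rate than the usable looks give.

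**Working it through.** **Number planned at 14/25**

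- Section 14.0: 15 + 8 + 15 + 6 = 44; less 8 myeloma = 36.
- Section 9.3: 3 × 15 + 6 = 51; less 15 myeloma = 36.

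Section 4.1 counts phase Ib patients treated at the MTD within the disease cohorts, so they do not raise the lymphoma figure. Any myeloma patients treated at 14/25 in phase Ib come on top of 36; the documents give no count.

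**Reproducing the plan's row**

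Let X15, X30 and X45 be cumulative DLTs, with independent patients and a common DLT rate p. The reduction probability is P(X15 ≥ 8) + P(X15 ≤ 7, X30 ≥ 16) + P(X15 ≤ 7, X30 ≤ 15, X45 ≥ r). The written third threshold, over 24, means r = 25. Exact values:

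| True DLT rate | Stated | Look 1 only | Looks 1 and 2 | Plus ≥25/45 (as written) | Plus ≥24/45 |
|---|---|---|---|---|---|
| 5% | 0.000 | 0.000 | 0.000 | 0.000 | 0.000 |
| 10% | 0.000 | 0.000 | 0.000 | 0.000 | 0.000 |
| 15% | 0.001 | 0.001 | 0.001 | 0.001 | 0.001 |
| 20% | 0.004 | 0.004 | 0.004 | 0.004 | 0.004 |
| 25% | 0.016 | 0.017 | 0.018 | 0.018 | 0.018 |
| 30% | 0.056 | 0.050 | 0.052 | 0.052 | 0.052 |
| 35% | 0.118 | 0.113 | 0.122 | 0.122 | 0.123 |
| 40% | 0.243 | 0.213 | 0.239 | 0.241 | 0.246 |
| 50% | 0.632 | 0.500 | 0.589 | 0.607 | 0.630 |

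Up to 40% every version is close to the printed row. At 50% the printed 0.632 is close to a threshold of 24 or more (0.630), not to the written threshold (0.607).

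**Can the third look trigger?**

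No crossing at 30 means at most 15 DLTs. With N patients at 14/25, the most DLTs possible at the end is 15 + (N − 30).

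- N = 36: 21, below 25.
- N = 39: 24, still below 25.
- N = 40: 25; at a 50% rate the probability is 0.589.
- N = 42: 27; at a 50% rate the probability is 0.591.

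With 36 to 39 patients the rule is exactly the two-look rule.

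**Size of the gap at 50%**

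- Stated less usable: 0.632 − 0.589 = 0.043.
- Lost third look, as written: 0.607 − 0.589 = 0.018.
- Printed figure against the written threshold: 0.632 − 0.607 = 0.025.

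**If myeloma DLTs are pooled into the looks**

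Assume, in proportion to 8/44, that 3 of the first 15 and 5 of the first 30 are myeloma patients (12 + 3, then 13 + 2), with a lymphoma DLT rate of 40%. The two-look probability is then:

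| Myeloma DLT rate (assumed) | 20% | 30% | 40% | 50% | 60% |
|---|---|---|---|---|---|
| Reduction probability | 0.140 | 0.187 | 0.239 | 0.295 | 0.355 |

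The documents give no myeloma DLT rate, so the direction of the effect is unknown.

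**Timing of look 2**

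The DLT window is 4 × 28 = 112 days, or 3.68 months. Section 16.0 expects about 2 patients a month plus 1 every other month from the other sites. That is 2.5 a month if the latter is a total, or 3.5 if it applies to each of three sites. Entries in one window are 3.68 × 2.5 = 9.2 to 3.68 × 3.5 = 12.9 patients. At an assumed lymphoma share of 36/44, that is 7.5 to 10.5 lymphoma patients, more than the 6 left after the 30th.

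**The case against.** The arithmetic is not in dispute; its weight is.

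- **The lost look changes no dose in this trial.** It falls after the last patient has finished and could only inform a later study. The looks at 15 and 30 are both reachable with 36 patients. This stands, and it limits the cost of the lost look to 1.8 points at 50% and 0.2 points at 40%.
- **Most of the 4.3 points is not caused by myeloma.** This stands: 2.5 points would remain with 45 patients all at 14/25.
- **The printed row may be simulated.** It departs from the exact values in both directions, and only its 50% entry clearly favours 24 or more. With 1,000 simulated trials (an assumption) the standard error near 0.607 is about 0.015, and 0.632 lies 1.6 standard errors away. So the cause of the mismatch is not settled, but 0.632 remains too high for the rule as written.
- **The natural reading already separates myeloma.** A patient starting at 10/25 cannot be reduced from 14/25, and Table 2a is specific to myeloma. That is the sensible reading, but the plan does not state it, and section 14.0 says the opposite by listing myeloma among those at the MTD.
- **The pooled range is hypothetical.** It holds the myeloma rate fixed, whereas at 60% the 2-of-6 rule would be met within six patients with probability 0.96 and the dose lowered. The upper values are therefore unlikely to persist.
- **Thirty-six is a floor.** Some myeloma patients may have received 14/25 before their dose was lowered. Even if all 8 had, the total would be 44, and the written threshold applied at that point gives 0.599 at a 50% rate, still short of 0.632.

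Individual dose holds, the myeloma step-down rule, the data and safety monitoring committee and the planned cohort analyses also protect patients.

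**Conclusion.** The concern holds and should be fixed. Sections 14.0 and 9.3 contradict each other on which patients are at the MTD. About 36 are planned at 14/25 whichever total is used, and the 45-patient threshold is out of reach for them. At a 50% DLT rate the usable rule reduces the dose with probability 0.589, not 0.632; up to 40% the change is at most 0.004. The numerical loss is small. The more important defect is that the rule does not say whose DLTs it counts. The probabilities assume independent patients with one common DLT rate. The pooled range and the timing estimate rest on the further assumptions stated with them.

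**What to change.** Keep the doses and the 8/15 and 16/30 boundaries, and amend section 14.0 as follows.

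1. Restate the number planned at 14/25 as about 36, plus any myeloma patients already treated at that dose. Reconcile the phase IIa totals (38 in section 4.1; 39, 44 and 45 in section 14.0; 51 in section 9.3) and the myeloma cohort size (8 or 15). The 36 holds under either size.
2. State that the rule counts only patients who start at 14/25, and that phase IIa myeloma is governed by section 9.3 and reported separately.
3. Make the 45-patient look an end-of-study summary. Replace the row, for rates of 5, 10, 15, 20, 25, 30, 35, 40 and 50%, with 0.000, 0.000, 0.001, 0.004, 0.018, 0.052, 0.122, 0.239 and 0.589. Print the look-1 values beside it: 0.000, 0.000, 0.001, 0.004, 0.017, 0.050, 0.113, 0.213 and 0.500.

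The look-1 values matter because, unless accrual pauses or the boundary is crossed early, look 2 may report after most or all of the last 6 patients have started. Protection during accrual is then closer to look 1 alone.

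The cost is one amended paragraph and a recomputed row, with no added patients. The drawback is that the figure at 50% becomes less favourable.
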